8.2 Overall Study Design

This study is a Phase 3, prospective, randomized, open-label, multicenter study to compare the safety and efficacy of PK and FVIII trough level-guided BAX 855 treatment targeting FVIII trough levels of 1-3% or approximately 10% (8-12%) in a total of 96 evaluable (48 in each of 2 study arms) adolescent and adult PTPs with severe hemophilia A (<1% FVIII). Approximately 116 subjects will be enrolled for a total of 96 evaluable subjects (assuming a dropout rate of close to 10% and 10-15% of subjects being non-compliant). Subjects from the BAX 855 continuation (261302) the BAX 855 surgery (261204) study, the BAX 855 pediatric (261202) study^v, and newly recruited subjects including BAX 855-naïve subjects will participate.

Subjects will be screened per protocol inclusion/exclusion criteria and, following confirmation of eligibility, will undergo an initial PK assessment following a single administration of BAX 855 (60 ±5 IU/kg) to determine PK parameters. Following the PK assessment, subjects will be randomized to one of 2 dosing regimens: the standard treatment arm will target FVIII trough levels of 1-3% and the second, intensified treatment arm will target trough levels of approximately 10% (8-12%) FVIII. The dose and frequency will be based on each subject's individual PK. More frequent dosing should be considered if single doses of >80 IU/kg are required or regular FVIII peak levels of 200% would be reached.

^v In case subject is at least 12 years of age at the time of informed consent of this study.

Subjects will complete study visits as follows to undergo efficacy, safety, and PRO assessments: Baseline Visit, Visit 1 at 4 weeks \pm 5 days; Visit 2 at 8 weeks \pm 1 week; Visit 3 at 3 months \pm 2 weeks; Visit 4 at 4.5 months \pm 2 weeks; Visit 5 at 6 months \pm 1 week (26 \pm 1 weeks); Visit 6 at 7.5 months \pm 2 weeks; Visit 7 at 9 months \pm 2 weeks; Visit 8 at 10.5 months \pm 2 weeks; and the Study Completion/Termination Visit for follow-up at 12 months \pm 1 week (53 [\pm 1] weeks). It must be ensured that the second 6-month study period will consist of at least 26 weeks following the 6 month-study visit scheduled at 26 (\pm 1) weeks and that the subject will have received his PK-tailored dosing regimen for at least 52 weeks. The following items are discussed with the subject at each study visit: concomitant medications, non-drug therapies, AEs, bleeding episodes and their treatment, including details of target joint bleedings, as well as any physical activity within 8 h prior to the onset of a bleeding episode, type and duration of physical activity with a risk category of 2.5 or higher ²⁹, or contact sport for a duration of 15 minutes or more, and to review the subject diary. For subjects without bleeding episodes, Visits 6 and 8 are phone visits. If, however, a subject has a bleeding episode, instead of a phone visit the subject must attend a site visit to assess FVIII trough levels and IR and re-evaluate the PK-guided regimen, the subject's physical activity and compliance. In these cases the subject will undergo all planned assessments for a study visit, including assessment of vital signs, physical examination, and all laboratory assessments.

The overall study design is illustrated in [Figure 1](#).

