14.4 Methods of Analysis

14.4.1 Primary Outcome Measure

The proportion of subjects with ABR = 0 in the 2 prophylaxis treatment regimens in the second 6 months period will be compared using a chi-square test with continuity correction at a 2-sided 5% level of significance.

The null hypotheses of no difference between the prophylactic regimens will be tested against a 2-sided alternative.

The observation period for the primary endpoint will be the second 6 months of prophylaxis (Day 183 to Day 364). If the subject undergoes a surgical procedure the observation period is interrupted starting from the presurgical loading dose until the subject resumes his previous prophylactic treatment regimen, or until rehabilitation or any other surgery specific postoperative measures have been completed, whichever occurs last.

Data analyses will follow the intent-to-treat principle, i.e., bleedings observed in the observation period will be used in the analyses irrespective of compliance with the treatment regimen of the protocol. Only if a subject refuses to provide any bleeding data, the multiple imputations (MI) technique will be used to handle observation periods shorter than 6 months, i.e., 182 days, as follows.

For subjects who terminated before Day 364 and refuse to provide data on bleeds, bleeds will be imputed for the unobserved period from a Poisson random variate. The subject specific Poisson parameter will be determined from estimating a negative binomial model for the bleed rate in the unobserved period with stratum, age, race as well as the number of bleeds from Day 92 to the end of the observed period of the subject as covariates in all subjects of the same Study Arm. For subjects with more than 21 weeks in the observation period, the number of bleeds occurring at a later time in other subjects might be very low or even zero. To avoid estimating from an unstable model, the negative binomial model will be for the number of bleed up to Day 329 with covariates of stratum, age, race and number of bleeds observed from Day 92 to Day 329. At least 1000 imputation datasets will be generated. The chi-squared test statistics with continuity correction and its standard error will be used to compare the 2 study arms in each imputation dataset and the multiple imputations techniques will be used to derive an overall estimate with 2-sided 95% CIs.

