5.3.2 Surgery Day

Surgery day (SDay) is a relative study day, calculated per surgical procedure for each subject as applicable. The day on which the subject receives pre-surgical loading dose is defined as SDay 1 for each respective surgery. SDay will then increase for every day after SDay 1 until the day before the subject resumes PK-guided prophylaxis in the PROPEL study.

To distinguish between SDays of different surgeries per subject, an additional variable will be assigned, indicating a specific surgery as the *i*'th chronologic surgery for the subject.

$$\text{Surgery Day} = (\text{Date of Event} - \text{Date of SDay 1})$$

Where date of event is any surgery related assessment or measurement performed.

For example, consider a subject that had two surgeries during the study and received pre-surgical loading dose on the same day as the surgery procedure. For the 1st surgery, the subject resumed regular PK-guided prophylaxis 3 days after the procedure and for the 2nd surgery, 4 days after the procedure. The subject would then have SDay running from 1 to 2 for the 1st surgery and SDay running from 1 to 3 for the 2nd surgery.

Surgery days/periods will be excluded for efficacy analyses purposes as if the subject left the study for surgery and returned to the study once regular PK-guided prophylaxis was resumed (as was the actual case for the 261302 study).

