- A subject is considered to be completed if the reason for termination indicates the subject completed the study. Otherwise the subject should be considered discontinued. For the first 6-month period, a subject is considered to be completed if not discontinued before or on ObsDay 182. For the second 6-month period, the subject needs to have a disposition or bleed record at or after ObsDay 364.

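### After more than about 14–15 surgical days the 53 ±1 week Completion Visit and the rule of 52 weeks on regimen cannot both be met, and neither document says which yields; the SAP's surgery-day count is also one day short

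*Protocol*

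**What the plan says.** Visits run on calendar time. Protocol 8.2 puts the 6-month visit at 26 ±1 weeks and "the Study Completion/Termination Visit for follow-up at 12 months", given also as 53 ±1 weeks. The next sentence sets two conditions: "It must be ensured that the second 6-month study period will consist of at least 26 weeks following the 6 month-study visit", and that "the subject will have received his PK-tailored dosing regimen for at least 52 weeks". Section 21.2 and the footnotes to 21.3 and 21.4 repeat both.

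The primary endpoint runs on observation time, Day 183 to Day 364. Under Protocol 14.4.1, if there is surgery, "the observation period is interrupted starting from the presurgical loading dose until the subject resumes his previous prophylactic treatment regimen", or until rehabilitation and similar measures are finished, if that is later. SAP 5.3.3 carries this out by subtracting surgery days (SDays) from ObsDay. Protocol 8.7.8 has the PK-tailored regimen resume only after any rehabilitation that needs intensified treatment.

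SAP 5.3.2 calls the day of the loading dose SDay 1, runs the count to the day before PK-guided prophylaxis resumes, and gives the formula as event date minus the date of SDay 1. In its first example (loading on the day of the procedure, resumption three days later), "The subject would then have SDay running from 1 to 2 for the 1st surgery".

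On completion, SAP 6.1 says: "For the second 6-month period, the subject needs to have a disposition or bleed record at or after ObsDay 364".

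**The concern.** Two clocks govern the end of follow-up, and only one stops during surgery. The calendar window gives a site a latest date. The 52-week condition, with surgical time not counted, can require a later one. Neither document says that the ±1 week tolerance may be exceeded for surgery, or that the 52-week condition may be waived.

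A site that follows the visit schedule closes the subject before ObsDay 364 although the subject never dropped out. The last part of the primary window is then not observed prospectively on the randomized regimen. Long interruptions are foreseeable: Protocol 22.1.1 lists hip and knee replacement, and 22.4 allows for intensified treatment during rehabilitation.

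The SDay count matters because it feeds the same clock. If it is one short, a day of surgical FVIII cover counts as a day of prophylaxis observation.

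**Working it through.** **The plan's own figures.** 364 − 183 + 1 = 182 days = 26 × 7, and 52 × 7 = 364. Both reproduce.

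**Limit on surgical days.** Let S be the SDays before the visit. From SAP 5.3.3, ObsDay = (visit date − reference date) + 1 − S. The visit window is 52, 53 or 54 weeks, so the date difference is 364, 371 or 378. ObsDay ≥ 364 requires:

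- week 52: 365 − S ≥ 364, so S ≤ 1
- week 53: 372 − S ≥ 364, so S ≤ 8
- week 54: 379 − S ≥ 364, so S ≤ 15

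If week 54 is read as study Day 378, each limit drops by one, to 0, 7 and 14. The 52-week condition gives the same limits: days on regimen are the elapsed days less S, and must reach 364.

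**Shortfall if the calendar window is kept.** The S values are illustrative; the documents give no expected durations.

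| S (days) | ObsDay at week 53 | Days short | ObsDay at week 54 | Days short (% of 182) |
|---|---|---|---|---|
| 8 | 364 | 0 | 371 | 0 |
| 15 | 357 | 7 | 364 | 0 |
| 16 | 356 | 8 | 363 | 1 (0.5%) |
| 28 | 344 | 20 | 351 | 13 (7.1%) |
| 42 | 330 | 34 | 337 | 27 (14.8%) |
| 84 | 288 | 76 | 295 | 69 (37.9%) |

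**If the gap is imputed.** Assume a constant bleed rate and that the planning proportions p (40% and 70% bleed-free) apply to the 182-day window. A subject bleed-free so far is then given at least one bleed over 27 days with probability 1 − p^(27/182): 12.7% at p = 0.40 and 5.2% at p = 0.70. This applies only if the subject also refuses bleed data.

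**How the SAP classifies a subject whose form says completed at week 54 but who is at, say, ObsDay 337.**

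- SAP 4.4 (per-protocol set): the second period counts as completed if the subject did not discontinue prematurely. This subject qualifies.
- SAP 6.1: completed overall by termination reason, but not for the second period without a record at or after ObsDay 364.
- SAP 5.5.1 (imputation): applies to premature discontinuation, explained as before ObsDay 364, with refusal of data. The first term excludes this subject; the explanation includes the subject.

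**SDay count.** Loading on date D, resumption on D+3. By the definition the surgical days are D, D+1 and D+2: three days, SDay 1 to 3. The formula gives 0, 1 and 2, and the example ends at 2. For the second operation (resumption on D+4) the definition gives four days and the example three. Subtracting 2 and 3 in place of 3 and 4 leaves one surgical day per operation in the observation period.

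**The case against.** A reader might infer that the visit is fixed and that a subject with long surgery cannot reach ObsDay 364. The documents do not support that. The 52-week condition is worded as an obligation and repeated as an instruction for planning the Completion Visit. With Protocol 8.7.8 it points to a later visit. What remains is that the stated ±1 week window contradicts it and no text ranks the two.

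A reader might also infer that real bleed data from willing subjects are discarded and replaced by Poisson draws. That is not supported either. SAP 5.4.2, 7.1.2, 7.1.2.1 and 7.1.2.2 bring in bleed data up to nominal ObsDay 364 from the continuation study or from the subject, and treat them as observed. Imputation is for refusal only (Protocol 14.4.1, SAP 5.5.1). This answers most of the concern about lost data, though not all of it. Data requested from leavers are collected after exit and without treatment details, and the continuation study explores different regimens (Protocol 6.4.2).

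Most operations should fit within the slack. The SAP's examples last three and four days, minor surgery is expected to need at most three days of surveillance (Protocol 22.1.2), and subjects needing major emergency surgery leave treatment or the study (9.3). The exposed group is therefore mainly elective major surgery with rehabilitation.

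The SDay definition in the text is clear, so a programmer could follow it and ignore the formula and examples. But the SAP should not require that choice.

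**Conclusion.** The two instructions conflict for any subject with more than about 14–15 surgical days (7–8 at nominal week 53), and the conflict is unresolved. Keeping to the calendar window shortens prospective follow-up. The SAP can usually recover the bleed data, but its rules do not agree on what such a subject is.

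The size depends on the length of the interruption, for which the documents give no figure: 13 days (7%) of the primary window for an assumed 28 days and 27 days (15%) for an assumed 42, both at week 54. The 12.7% and 5.2% imputation probabilities need a long interruption, an early visit and refusal together. The number affected cannot be computed and is probably small. With 48 evaluable subjects per arm, one changed outcome moves a proportion by 1/48 = 2.1 percentage points.

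The SDay formula and both examples are wrong against the SAP's own definition, by one day per operation. The effect is slight, but it enters the primary clock. Both points merit correction because the repair is wording only; neither undermines the primary comparison.

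**What to change.** - **Protocol 8.2, 21.2 and the footnotes to 21.3 and 21.4:** state that after a surgical interruption the Completion Visit is held no earlier than ObsDay 365, that is, 53 ±1 weeks plus the interrupted days, so that the 52-week rule prevails over the calendar window. For 42 days this gives 58 to 60 weeks; at week 58, ObsDay = 406 + 1 − 42 = 365.
- **Protocol 11.1:** it bounds the primary period by the 6-month and Completion Visits; align it with Day 183 to Day 364.
- **Protocol 14.4.1 and SAP 5.3.2:** reconcile when the interruption ends (the later of resumption and completed rehabilitation, against resumption alone).
- **SAP 4.4, 5.5.1 and 6.1:** say in the same terms how a subject who finishes before ObsDay 364 because of surgery is treated.
- **SAP 5.3.2:** use (Date of Event − Date of SDay 1) + 1, and correct the examples to SDay 1–3 and 1–4.

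The cost is wording in both documents. The downside is that the few subjects with surgery stay in the study longer by the length of their interruption.

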8.3 Duration of Study Period(s) and Subject Participation

The overall duration of the study is approximately 3 years from study initiation (i.e., first subject enrolled) to study completion. The recruitment period is expected to approximately 16 months.

The subject participation period is approximately 15-16 months from enrollment to subject completion (i.e., last study visit), unless prematurely discontinued.

8.4 Outcome Measures

8.4.1 Primary Outcome Measure

The primary outcome measure is the presence or absence of any bleedings in the second 6-month study period.

8.4.2 Secondary Outcome Measures

8.4.2.1 Efficacy

1. Total, spontaneous, and traumatic ABR, and spontaneous AJBR
2. Total weight-adjusted consumption of BAX 855
3. Overall hemostatic efficacy rating at 8 (\pm 1) hours after the initiation of treatment and at resolution of bleed.
4. Number of BAX 855 infusions needed for the treatment of bleeding episodes
5. HJHS
6. Intra-, post- and perioperative hemostatic efficacy in case of surgery
7. Intra- and postoperative blood loss in case of surgery

8.4.2.2 Safety

1. Occurrence of AEs and serious adverse events (SAEs)
2. Clinically significant changes in vital signs and clinical laboratory parameters (hematology, clinical chemistry, and lipids)
3. Inhibitory antibodies to FVIII, and binding antibodies to FVIII, BAX 855, PEG, and CHO protein

8.4.2.3 Patient Reported Outcomes

1. Physical domain and component scores of the SF-36 Health Survey

8.4.2.4 Pharmacokinetics

1. BAX 855 PK parameters based on FVIII activity at baseline and steady state, if applicable:
 - AUC_{0-∞} (area under the plasma concentration versus time curve from time 0 to infinity), IR (incremental recovery) at 15-30 minutes post-infusion, T_{1/2}, MRT, CL (clearance), maximum plasma concentration (C_{max}) and time to maximum concentration in plasma (T_{max}), V_{ss} (Volume of distribution at steady state)
 - Incremental recovery (IR) over time

8.4.3 Exploratory Outcome Measures

1. Thrombin generation assay (TGA) parameters (lag time, time to peak thrombin generation, peak thrombin generation, and endogenous thrombin potential [ETP])
2. Bleed and pain severity scores as measured by the Haemo-SYM questionnaire
3. HRQoL as assessed using EQ-5D and mental domain and component scores of SF-36
4. Health resource utilization

8.5 Randomization and Blinding

This is a randomized, open-label, concurrent, dose regimen comparison clinical study. In order to minimize/avoid bias, once eligibility is confirmed, subjects will be randomly assigned to one of 2 treatment regimens with PK-guided dosing targeting FVIII trough levels of 1-3% or approximately 10% (8-12%) in a 1:1 ratio. Randomization occurs after the PK assessment and will be stratified according to subjects' pre-study treatment regimen/ABR (prophylaxis with ABR <5 vs. prophylaxis with ABR ≥5 vs. on-demand).

8.6 Study Stopping Rules

This study will be halted (enrollment and treatment temporarily stopped), pending further review by sponsor, or stopped if the following criterion is met:

- If 2 or more subjects develop a high responder inhibitory antibody >5 BU, confirmed by 2 measurements within a 2-4 week period at the central laboratory, after BAX 855 administration
- If 2 or more subjects develop anaphylaxis following exposure to BAX 855

The study may be terminated, if 1 or more of the following criteria are met:

- The sponsor decides to terminate the study based upon its assessment of safety
- The sponsor decides to terminate the study for administrative reasons

8.7 Investigational Product(s)

8.7.1 Packaging, Labeling, and Storage

BAX 855 is formulated as a sterile, highly purified protein preparation in lyophilized form for i.v. infusion and is provided in single-dose vials with a vial of diluent (2 mL or 5 mL SWFI, as available). A butterfly transfer set with luer-lock syringes and a needleless transfer device (BAXJECT II high-flow [HF] or BAXJECT III, as available) will be used for reconstitution and bolus i.v. delivery. The BAXJECT system is a needleless liquid transfer device with the primary function of transferring diluent from its vial into an evacuated vial containing product requiring reconstitution prior to infusion.

A minimum of 4 lots of BAX 855 manufactured for this study will be used. Four potencies of BAX 855 may be used, depending upon availability: 250, 500, 1,000 and 2,000 IU/vial. Additional potencies of 750 IU/vial, 1500 IU/vial and 3000 IU/vial will be used once available.

The recommended storage conditions for BAX 855 are 2°C to 8°C (36°F to 46°F) and it should not be allowed to freeze. BAX 855 should be stored and protected from light.

The reconstituted product should ideally be used immediately but no longer than 3 hours after reconstitution.

For additional information, such as reconstitution instruction, please refer to the BAX 855 IB and/or other specific instructions provided by the sponsor.

8.7.2 Administration

Following reconstitution, BAX 855 should be administered using plastic syringes provided by the sponsor since proteins such as BAX 855 may adhere to the surface of glass syringes. BAX 855 will be administered i.v. using an appropriately sized syringe, as a bolus infusion with a maximum infusion rate of 10 mL/min, as described in the BAX 855 IB. The reconstituted BAX 855 must be administered at room temperature and within 3 hours.

BAX 855 dose calculation will be based on the stated actual potency of each vial.

PK assessment and determination of IR

For the PK assessment in individual subjects (initial and at steady state, if applicable), only vials of the same lot with a nominal potency of 500 IU should preferably be used. If due to a subject's weight, the PK or IR infusion volume will exceed 30 mL, 1000 IU vials should preferably be used to reduce the volume administered.

The total calculated dose may be rounded up or down to the nearest whole vial in case 500 IU potency vials are used. However, in case vials with a nominal potency of 1,000 IU/vial are used, the total calculated dose should not be rounded up or down to the nearest whole vial to ensure accurate dosing (e.g., 2.5 vials).

In approximately 30 subjects who have a PK-guided prophylactic dose of ≥ 40 IU/kg, at least one IR following baseline IR should be determined using vials with a nominal potency of 3000 IU, once available. The total calculated dose should not be rounded up or down to the nearest whole vial to ensure accurate dosing. Only vials of the same lot should be used for one IR infusion.

Infusions for prophylaxis and treatment of bleeding episodes

All available potencies will be used for prophylaxis and treatment of bleeding episodes. Two different lots per infusion may be used, however, each vial must be reconstituted with its own kit. The total calculated dose can be rounded up or down to the nearest whole vial.

8.7.3 Description of Treatment

Subjects will be randomized to one of 2 PK-tailored prophylactic dose regimens (see Section 8.5) each of them targeting:

- FVIII trough levels of 1-3% with approximately twice weekly dosing, or
- FVIII trough levels of approximately 10% (8-12%) with dosing approximately every other day.

The individual subject's dose will be calculated by the sponsor and provided to the study site. Depending on subject's individual PK, different dosing intervals should be considered if single doses of >80 IU/kg are required or regular FVIII peak levels of 200% would be reached or exceeded.

8.7.4 BAX 855 Dosing for PK Assessment

Following a 72-96 h washout period, depending on the FVIII concentrate, subjects will undergo an initial PK assessment with BAX 855^{vi}:

At Visit 9 months, i.e., after 9 months of prophylactic treatment with BAX 855, an optional repeat PK at steady state will be performed. No washout period will be required prior to the optional repeat PK determination; however, the PK infusion should preferably coincide with the prophylactic treatment schedule to ensure that the baseline FVIII trough level is reached.

The BAX 855 dose to be used for the PK assessment is 60 ± 5 IU/kg. It must be administered in the hospital/clinic setting under medical supervision.

